17.1 Sample size calculation

The sample size calculation has been determined taking the small patient population into account, while also aiming for an acceptably narrow 95% confidence interval for the ABR.

Sufficient inference on bleeding episodes for the primary CPoC criterion is judged to be accommodated by 30 patients.

It is expected that the treatment duration of the main part allowing for escalation time for some patients is on average 6 months in the below calculations.

When evaluating the power of the negative binomial analysis referred above, an annual bleeding rate of 4 is assumed for the end dose concizumab regimen, respectively in combination with an over-dispersion of 6. The power for concluding a bleeding rate lower than 12 then becomes approximately 95%. The power under varying values of true ABR and over-dispersion for the primary CPoC criterion are shown below in [Table 17-1](#).

Table 17-1 Power in comparison between concizumab prophylaxis treatment and an ABR threshold of 12 under different assumptions of ABR and over-dispersion.

Power	Over-dispersion		
	5	6	7
4	99%	95%	92%
5	95%	90%	86%
6	87%	81%	72%

Protocol
 Trial ID:NN7415-4255
 UTN:U1111-1179-3872
 EudraCT no.:2016-000614-29

~~CONFIDENTIAL~~

Date:	15 March 2017	Novo Nordisk
Version:	1.0	
Status:	Final	
Page:	100 of 122	

For the secondary CPoC criterion that includes data prior to potential dose escalation, it is expected that the treatment duration of the main part is on average 8 months with an average ABR of 5.4 for the concizumab treated patients. This yields a marginal power of approximately 87% for the secondary CPoC criterion.

In prior Novo Nordisk trials conducted in haemophilia patients, the typical 1-year over-dispersion for non-inhibitor patients on prophylaxis with FVIII or FIX has been in the range 4-8, implying 24 weeks over-dispersion of 3-5 (e.g. in NN7008-3543, NN7088-3859 and NN7999-3747). On that background, an over-dispersion of 6 over the 24 weeks in the main part of the current trial is deemed realistic.

17.2 Definition of analysis sets

All dosed patients will be included in the Full Analysis Set (FAS) as well as in the Safety Analysis Set (SAS).

17.3 Primary endpoint

The primary endpoint is the number of bleeding episodes during at least 24 weeks from treatment onset.

The primary endpoint will be estimated using negative binomial regression with log of *exposure time in main phase* as offset, providing an actual estimate of the ABR as well as a corresponding 95% confidence interval.

This analysis has the underlying assumption that the missing data mechanism is “missing at random”, i.e. MAR. Under this assumption, the statistical behaviour of the missing data (given the observed responses and the mean value structure) is assumed to be the same as for the observed data. The endpoint will be estimated based on the full analysis set (FAS) and only data collected prior to discontinuation of trial product or initiation of alternative treatment options will be used to draw inference.

17.4 Sensitivity analyses

To evaluate the robustness of the MAR assumption implied in the primary analysis, a modified tipping point analysis will be performed where patients having discontinued before finalization of the main part are assumed to have a worse outcome compared to what was observed during the main part of the trial. This will be done by adding a value Δ_i to the observed bleeding episodes in the main part of the trial before analysing the data. The offset is maintained as being the exposure during the main phase since it is not possible to identify the amount of missing observation time. The degree of worsening, Δ_i , will gradually be increased to evaluate at which point the upper 95% confidence limit of the prophylactic concizumab ABR is no longer below a threshold of 12.

Protocol
 Trial ID:NN7415-4255
 UTN:U1111-1179-3872
 EudraCT no.:2016-000614-29

~~CONFIDENTIAL~~

Date: 15 March 2017
 Version: 1.0
 Status: Final
 Page: 101 of 122

Novo Nordisk

The results of the primary analysis will be considered robust if the tipping point is above what is considered clinical plausible.

17.5 Additional analyses

An additional evaluation of the primary endpoint will be made, including actual concizumab dose level as *additional factor in the primary analysis model specified above*. Point estimates and 95% confidence interval will be provided for the ABR at the different dose levels of concizumab (0.15, 0.20 and 0.25 mg/kg). Furthermore, an analysis with individual steady state PK/PD assessments included as covariates in the negative *binomial regression model as specified for the primary analysis* will be performed in order to evaluate possible associations between PK/PD and ABR that potentially could guide dose-selection. The referred steady-state PK/PD assessments comprise the concizumab trough level, maximum plasma concentration (C_{max}) of concizumab, TFPI value prior to the last s.c. dose administration, peak thrombin generation (nM), Endogenous thrombin potential (nM*min) and velocity index (nM/min).

17.6 Secondary endpoints

17.6.1 Supportive secondary efficacy endpoints

- The number of bleeding episodes during 76 weeks from treatment onset.
- The number of spontaneous bleeding episodes during at least 24 weeks from treatment onset.
- The number of spontaneous bleeding episodes during 76 weeks from treatment onset.

The supportive secondary endpoints will be estimated using the same negative binomial regression model as the primary endpoint.

17.6.2 Supportive secondary safety endpoints

- Number of treatment-emergent adverse events (TEAEs) during at least 24 weeks from treatment onset
- Number of TEAEs during 76 weeks from treatment onset.
- Occurrence of anti-concizumab antibodies during at least 24 weeks from treatment onset.
- Occurrence of anti-concizumab antibodies during 76 weeks from treatment onset.
- Change from baseline of fibrinogen during 24 weeks from treatment onset.
- Change from baseline of fibrinogen during 76 weeks from treatment onset.

Protocol
 Trial ID:NN7415-4255
 UTN:U1111-1179-3872
 EudraCT no.:2016-000614-29

~~CONFIDENTIAL~~

Date: 15 March 2017
 Version: 1.0
 Status: Final
 Page: 102 of 122

Novo Nordisk

- Change from baseline of D-dimer during 24 weeks from treatment onset.
- Change from baseline of D-dimer during 76 weeks from treatment onset
- Change from baseline of prothrombin fragment 1 + 2 (F1 + 2) during 24 weeks from treatment onset.
- Change from baseline of F1 + 2 during 76 weeks from treatment onset.
- Change from baseline of prothrombin time (PT) during 24 weeks from treatment onset.
- Change from baseline of PT during 76 weeks from treatment onset.
- Change from baseline of activated partial thromboplastin time (APTT) during 24 weeks from treatment onset.
- Change from baseline of APTT during 76 weeks from treatment onset.
- Change from baseline of antithrombin (AT) during 24 weeks from treatment onset.
- Change from baseline of AT 76 weeks from treatment onset.

Adverse Events will be coded using the most recent version of Medical Dictionary for Regulatory Activities (MedDRA) coding.

A Treatment Emergent Adverse Event (TEAE) is defined as an event that has onset from the first exposure to treatment until the last visit in the trial. Treatment-emergent adverse event endpoints will be summarised by system organ class, preferred term, seriousness, severity and relation to trial product. All Adverse events will further be listed.

Frequency of binding anti-concizumab antibodies will be listed and summarised by time frame according to the two endpoint definitions.

All laboratory safety endpoints will be plotted by time, both as absolute values and change from baseline. Laboratory safety endpoints will further be summarised and listed.

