1.0
Final
12 of 122

Novo Nordisk

PK	pharmacokinetic
PP	per protocol
PRO	patient reported outcome
PT	prothrombin time
QA	quality assurance
Q4D	every 4 th day
rFVIII	the name 'rFVIII' will be used throughout the protocol and the product is identical to 'turoctocog alfa'
SAE	serious adverse event
SAS	safety analysis set
sBE	spontaneous Bleeding Episode
s.c.	subcutaneous(-ly)
SI	international system of units
SmPC	summary of product characteristics
SUSAR	suspected unexpected serious adverse reaction
TEAE	treatment emergent adverse events
TIA	transient ischemic attack
TF	tissue factor

Protocol
Trial ID:NN7415-4255
UTN:U1111-1179-3872
EudraCT no.:2016-000614-29

~~CONFIDENTIAL~~

Date:
Version:
Status:
Page:

15 March 2017
1.0
Final
13 of 122

Novo Nordisk

TFPI	tissue factor pathway inhibitor
TG	thrombin generation
TMM	trial materials manual
TPA	trial product administration
UTN	Universal Trial Number

Protocol
Trial ID: NN7415-4255
UTN: U1111-1179-3872
EudraCT no.: 2016-000614-29

~~CONFIDENTIAL~~

Date: 15 March 2017
Version: 1.0
Status: Final
Page: 14 of 122

Novo Nordisk

1 Summary

The main objective for the phase 2 trial NN7415-4255, explorerTM5, is to assess the efficacy of concizumab administered s.c. once daily to prevent bleeding episodes in patients with severe haemophilia A without inhibitors. Furthermore, this trial aims to assess the longer-term efficacy and safety of concizumab in severe haemophilia A patients without inhibitors.

Objective(s) and endpoint(s):

Primary objective

- To assess the efficacy of concizumab administered s.c. once daily in preventing bleeding episodes in patients with severe haemophilia A without inhibitors

Secondary objectives

- To assess the longer-term efficacy of concizumab in patients with severe haemophilia A without inhibitors
- To assess the safety of concizumab in patients with severe haemophilia A without inhibitors
- To assess the immunogenicity of concizumab in patients with severe haemophilia A without inhibitors

Primary endpoint

- The number of bleeding episodes during at least 24 weeks from treatment onset..

Key secondary endpoints

- The number of spontaneous bleeding episodes during at least 24 weeks from treatment onset
- The number of treatment emergent adverse events (TEAEs) during at least 24 weeks from treatment onset.

Time frames for evaluation of objectives/endpoints:

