- Informed consent obtained before any trial-related activities. Trial-related activities are any procedures that are carried out as part of the trial, including activities to determine the suitability for the trial
- Male patients aged ≥ 18 years at the time of signing informed consent, diagnosed with severe haemophilia A (FVIII activity $< 1\%$), based on medical records or results at screening

Key exclusion criteria

- Known or suspected hypersensitivity to trial product(s) or related products
- Known inherited or acquired bleeding disorder other than haemophilia A
- Presence of inhibitors (neutralising antibodies) to Factor VIII (≥ 0.6 Bethesda Units) at screening measured by the Nijmegen method

Key Efficacy assessment

- The number of bleeding episodes during at least 24 weeks.

Protocol
Trial ID:NN7415-4255
UTN:U1111-1179-3872
EudraCT no.:2016-000614-29

~~CONFIDENTIAL~~

Date: 15 March 2017
Version: 1.0
Status: Final
Page: 16 of 122

Novo Nordisk

Key Safety assessment

- Number of TEAEs during at least 24 weeks.

Trial product(s):

The following products will be used in the trial:

- **Investigational Medicinal Product (IMP):**
Concizumab B, 100 mg/mL to be administered s.c. with NovoPen[®] 4 and needles
- **Non Investigational Medical Product (NIMP):**
Turoctocog alfa (rFVIII) 2000 IU/vial and isotonic sodium chloride (solvent). Turoctocog alfa (rFVIII) is for intravenous administration.

Table 2-2 Flow chart explanatory descriptions

Footer	Description
a	Concizumab administration is performed at home except for visit 2 where concizumab administration will take place at the trial site.
b	The duration of the visits will last according to patient's individual training need on concizumab administration, NovoPen [®] 4, eDiary training etc. Visit 3 will be a phone call to the patient.
c	For patients being dose escalated a phone call is recommended 1 week after first new dose of concizumab.
d	Daily dosing preferably at the same time in the morning.
e	Evaluation of laboratory results obtained from samples taken at screening.
f	Bleeding episodes occurring between visit 1 and visit 2 or at site should be registered in the eCRF. All bleeding episodes except for severe occurring after visit 2 at home should be registered in the eDiary. Severe bleeding episodes must be registered in the eCRF.
g	Turoctocog alfa will be given to treat breakthrough bleeding episodes either in the clinic or at home.

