8.1.9 Treatment period - Main part

8.1.9.1 Visit 2 (Assessment, 1st concizumab treatment at site)

Visit 2 should be scheduled 14 to 21 days after visit 1. The date of visit 2 will be considered as trial day 1.

Before any concizumab administration it is important to verify the in/exclusion criteria again and review central laboratory test results from screening.

The patient must be in a non-bleeding state at the time of first administration with concizumab and should not have received any FVIII treatment for prophylaxis or for treatment of a bleeding episode within a period of 48 hours prior to dosing.

Patients will be asked to complete the ePRO questionnaires before any other trial related activities are performed according to section [8.6.1](#);

- Hemo-TEM,
- SF-36v2,
- SDS,
- TSQM,
- SIAQ-ISRQ

All protocol assessments must be performed before 1st administration of concizumab. Vital signs must be assessed both before and after concizumab administration.

Assessment results from concomitant medication, vital signs, Body measurements (weight only) and details of adverse events must be entered into the eCRF.

At this, the 1st treatment visit, the allocated dose of concizumab will be given. Concizumab will be administered at the trial site supervised by medically trained trial staff.

Protocol
 Trial ID:NN7415-4255
 UTN:U1111-1179-3872
 EudraCT no.:2016-000614-29

~~CONFIDENTIAL~~

Date: 15 March 2017
 Version: 1.0
 Status: Final
 Page: 45 of 122

Novo Nordisk

The time point at which the completion of the first dose takes place corresponds to Time on treatment = 0 and must be recorded in the eCRF.

The patient must be observed at the trial site for at least 2 hours after the administration of the first dose of concizumab.

In order to determine the correct amount of the patient's daily dose of concizumab, until next scheduled visit, investigator will consult the dosing-table in the TMM on basis of the patient's current body weight.

Investigator will communicate any the daily dose of concizumab to the patient and record the dose for the coming home treatment period in the eCRF.

Prior to the first dose a dispensing call must be performed in the IWRS.

At the visit the patient will be provided with trial product (concizumab and if necessary rFVIII (turoctocog alfa)) and injection kits as well as an eDiary device to be able to conduct and report home treatment until the next scheduled visit.

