12.1 Definitions

12.1.1 Adverse event

An adverse event (AE) is any untoward medical occurrence in a patient administered a medicinal product, and which does not necessarily have a causal relationship with this treatment.

An AE can therefore be any unfavourable and unintended sign (including an abnormal laboratory finding), symptom or disease temporally associated with the use of a product, whether or not considered related to the product.

An AE includes:

- A clinically significant worsening of a concomitant illness.
- A clinical laboratory adverse event (CLAE): a clinical laboratory abnormality which is clinically significant, i.e. an abnormality that suggests a disease and/or organ toxicity and is of a severity that requires active management. Active management includes active treatment or further investigations, for example change of medicine dose or more frequent follow-up due to the abnormality.

The following should **not** be reported as AEs:

- Pre-existing conditions, including those found as a result of screening or other trial procedures performed before exposure to trial product (pre-existing conditions should be reported as medical history or concomitant illness).
- Pre-planned procedures unless the condition for which the procedure was planned has worsened from the first trial related activity after the patient has signed the informed consent.
- Bleeding episodes and other symptoms (e.g. pain, swelling, synovitis, arthralgia, injection site haematoma) in connection with bleeding episodes should not be reported as AEs/SAEs unless the event is fatal, life-threatening or evaluated by the investigator as related to trial product or trial procedure. All bleeding episodes and other findings related to underlying disease will be captured in the eCRF/eDiary

The following three definitions are used when assessing an AE:

- **Severity**
 - **Mild** – no or transient symptoms, no interference with the patient’s daily activities.
 - **Moderate** – marked symptoms, moderate interference with the patient’s daily activities.
 - **Severe** – considerable interference with the patient’s daily activities; unacceptable.
- **Causality**
 Relationship between an AE and the relevant trial product(s):
 - **Probable** - Good reason and sufficient documentation to assume a causal relationship.

Protocol
 Trial ID:NN7415-4255
 UTN:U1111-1179-3872
 EudraCT no.:2016-000614-29

~~CONFIDENTIAL~~

Date:	15 March 2017	Novo Nordisk
Version:	1.0	
Status:	Final	

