12.2 Reporting of adverse events

All events meeting the definition of an AE must be collected and reported. This includes events from the first trial-related activity after the patient has signed the informed consent until the end of the post-treatment follow-up period (visit 17). The events must be recorded in the applicable eCRF forms in a timely manner, see timelines below and [Figure 12-1](#)

During each contact with the trial site staff, the patient must be asked about AEs and technical complaints, for example by asking: “Have you experienced any problems since the last contact?”

All AEs, either observed by the investigator or patient, must be reported by the investigator and evaluated. All AEs must be recorded by the investigator on an AE form. The investigator should report the diagnosis, if available. If no diagnosis is available, the investigator should record each sign and symptom as individual AEs using separate AE forms.

For SAEs, a safety information form must be completed in addition to the AE form. If several symptoms or diagnoses occur as part of the same clinical picture, one safety information form can be used to describe all the SAEs.

AESIs regardless of the seriousness, must be reported using the AE form and safety information form

Protocol
 Trial ID: NN7415-4255
 UTN: U1111-1179-3872
 EudraCT no.: 2016-000614-29

~~CONFIDENTIAL~~

Date: 15 March 2017 | **Novo Nordisk**
 Version: 1.0
 Status: Final
 Page: 86 of 122

For all non-serious AEs, the applicable forms should be signed when the event is resolved or at the end of the trial at the latest.

Timelines for initial reporting of AEs:

The investigator must complete the following forms in the case report form (CRF)/eCRF within the specified timelines:

- **SAEs:** The AE form **within 24 hours** and the safety information form **within 5 calendar days** of the investigator’s first knowledge of the SAE.

[figure not shown]
Both forms must be signed within 7 calendar days from the date the information was entered in the eCRF.

For SAEs requiring reporting on a specific event form: In addition to the above the specific event form within **14 calendar days** from the investigator’s first knowledge of the AE.

- **Non-serious AEs fulfilling the AESI criteria:** The AE form and safety information form **within 14 calendar days** of the investigator’s first knowledge of the event.

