12.2 Reporting of adverse events

All events meeting the definition of an AE must be collected and reported. This includes events from the first trial-related activity after the patient has signed the informed consent until the end of the post-treatment follow-up period (visit 17). The events must be recorded in the applicable eCRF forms in a timely manner, see timelines below and [Figure 12-1](#)

During each contact with the trial site staff, the patient must be asked about AEs and technical complaints, for example by asking: “Have you experienced any problems since the last contact?”

All AEs, either observed by the investigator or patient, must be reported by the investigator and evaluated. All AEs must be recorded by the investigator on an AE form. The investigator should report the diagnosis, if available. If no diagnosis is available, the investigator should record each sign and symptom as individual AEs using separate AE forms.

For SAEs, a safety information form must be completed in addition to the AE form. If several symptoms or diagnoses occur as part of the same clinical picture, one safety information form can be used to describe all the SAEs.

AESIs regardless of the seriousness, must be reported using the AE form and safety information form

Protocol
 Trial ID: NN7415-4255
 UTN: U1111-1179-3872
 EudraCT no.: 2016-000614-29

~~CONFIDENTIAL~~

Date: 05 May 2017 | **Novo Nordisk**
 Version: 2
 Status: Final
 Page: 87 of 124

For all non-serious AEs, the applicable forms should be signed when the event is resolved or at the end of the trial at the latest.

Timelines for initial reporting of AEs:

The investigator must complete the following forms in the case report form (CRF)/eCRF within the specified timelines:

- **SAEs:** The AE form **within 24 hours** and the safety information form **within 5 calendar days** of the investigator's first knowledge of the SAE.

[figure not shown]
Both forms must be signed within 7 calendar days from the date the information was entered in the eCRF.

For SAEs requiring reporting on a specific event form: In addition to the above the specific event form within **14 calendar days** from the investigator's first knowledge of the AE.

- **Non-serious AEs fulfilling the AESI criteria:** The AE form and safety information form **within 14 calendar days** of the investigator's first knowledge of the event.

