The investigator must ensure that the recording of the worst case severity and seriousness of an event is kept throughout the trial. A worsening of an unresolved AE must be reported as follow up with re-assessment of severity and/or seriousness of the event.

Queries or follow-up requests from Novo Nordisk must be responded to **within 14 calendar days** from the date of receipt of the request, unless otherwise specified in the follow-up request.

SAEs after end of trial: If the investigator becomes aware of an SAE with a suspected causal relationship to the investigational medicinal product occurring to a patient after the patient has ended the trial, the investigator should report this SAE within the same timelines as for SAEs during the trial.

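### An adverse event that starts before the first dose and worsens on concizumab is left out of the TEAE count, because a TEAE is defined by onset alone and a worsening is filed as follow-up

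*Protocol*

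**What the plan says.** Protocol section 17.6.2 states that a TEAE "is defined as an event that has onset from the first exposure to treatment until the last visit in the trial". It has no clause for an event that began earlier and got worse. TEAEs are to be summarised by system organ class, preferred term, seriousness, severity and relation to trial product; all AEs are also listed.

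Section 12.2 sets the collection period: "events from the first trial-related activity after the patient has signed the informed consent until the end of the post-treatment follow-up period". Section 8.1.9.1 places the first dose two to three weeks after screening: "Visit 2 should be scheduled 14 to 21 days after visit 1".

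Section 12.3 fixes how a change is recorded: "A worsening of an unresolved AE must be reported as follow up with re-assessment of severity and/or seriousness of the event". The worst severity and seriousness are kept on the record.

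Section 12.1.1 includes among AEs "A clinically significant worsening of a concomitant illness". Section 8.2.2 defines a concomitant illness as one present at the first visit or found by a trial procedure before first exposure.

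The Summary (section 1) lists as a key secondary endpoint "The number of treatment emergent adverse events (TEAEs) during at least 24 weeks from treatment onset" and as the key safety assessment "Number of TEAEs during at least 24 weeks". Sections 4.2.2.1 and 17.6.2 call the same endpoint supportive secondary. All of this wording is the same in protocol versions 1.0 and 2.

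**The concern.** Each rule is reasonable alone; their combination leaves a gap. An AE can start between consent and the first dose. If it is unresolved at dosing and then worsens, section 12.3 updates the existing record and creates no new event with an on-treatment onset. Section 17.6.2 looks only at onset, so the event is not a TEAE however severe it becomes.

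At stake is a descriptive safety endpoint in a small single-arm trial of a drug for which section 18.1 names thromboembolic events as a potential risk. The events excluded are those that got worse after treatment started, so the omission always lowers the count.

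**Working it through.** The plan states no figure for this point, so there is none to reproduce. The check is to follow one event through the rules, for three kinds of pre-dose condition.

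| Condition before first dose | How it is recorded | What a worsening on concizumab becomes | Counted as TEAE? |
|---|---|---|---|
| Illness present at visit 1 | Concomitant illness (8.2.2) | A new AE if clinically significant (12.1.1) | Yes |
| Finding from a pre-dose trial procedure | Concomitant illness (8.2.2) | A new AE if clinically significant (12.1.1) | Yes |
| Event arising between visits 1 and 2 and reported as an AE | AE with pre-dose onset (12.2) | Follow-up of the same AE (12.3) | No (17.6.2) |

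Only the third row falls through. The second row is not fully clean either. Assessments at visit 2 are made before the first dose (8.1.9.1), yet sections 8.4.3 and 8.5.2.2 send abnormal vital signs and haematology results seen after screening to AE reporting. A finding first made at visit 2 before dosing can thus be read into the second row or the third.

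**Direction.** Every event with on-treatment onset is also in a definition that adds on-treatment worsening. The current count is therefore never higher than the wider one.

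**Size of the window.** Inputs: 33 patients planned to be dosed (section 6.1), 14 to 21 days from visit 1 to visit 2 (section 8.1.9.1), and a main part of at least 24 weeks, or 168 days.

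- Pre-dose time: 33 × 14 = 462 and 33 × 21 = 693 patient-days. Divided by 365.25, this is 1.26 to 1.90 patient-years.
- Minimum main-part time, if all 33 complete 24 weeks: 33 × 168 = 5,544 patient-days, or 15.2 patient-years.
- Ratio: 462/5,544 = 8.3% and 693/5,544 = 12.5%.

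**Number of events.** This needs an AE rate and a share that are unresolved and worsen, and the documents give neither. Purely as an illustration, assume 2 to 5 AEs per patient-year and a share of 10% to 25%. Then 1.26 × 2 = 2.5 to 1.90 × 5 = 9.5 AEs start before dosing, and 2.5 × 0.10 = 0.25 to 9.5 × 0.25 = 2.4 of them would be missed. The conclusion does not depend on this range.

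**The case against.** The strongest reply is that nothing here is contradictory. One record per event and an onset-based TEAE are compatible conventions, the endpoint is descriptive, and proof of concept rests on the bleeding rate. Most pre-dose conditions are handled by the concomitant-illness rule, and eligibility is verified again before dosing at visit 2, which removes some patients with a new problem. A non-serious AE that becomes serious must be reported within 24 hours, and one that comes to meet the criteria for special interest within 14 days (12.3). The enrolment-hold rules (12.7) and data monitoring committee review (12.8.2) do not depend on TEAE status.

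All of this stands, and it limits the point to tabulation. It does not close the gap, because an AE arising between visits 1 and 2 is outside the concomitant-illness rule and the protocol itself fixes the TEAE definition.

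A reader might infer more than the documents support:

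- That safety information is lost. It is not: the worst severity stays on the record, and all AEs are listed.
- That TEAE tables are the only AE summaries planned. Section 17.7.1 also summarises AEs related to technical complaints, and a statistical analysis plan, not available here, may add others.
- That this is without qualification the key secondary safety endpoint. Only the Summary uses that word.

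**Conclusion.** The point holds in a narrow form. Sections 12.2, 12.3 and 17.6.2 together exclude from the TEAE count, and from its summaries by seriousness, severity and relation, any AE recorded between consent and first dose that is unresolved and worsens on concizumab. The effect can only flatter the drug. It is probably small: the window is about 8% to 13% of the minimum main-part exposure, only unresolved events matter, and zero affected events is plausible. This rests on reading section 12.3 as written, so that follow-up leaves the onset date unchanged. It is a correction to the definition of one endpoint and no sign that safety surveillance is deficient.

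**What to change.** In section 17.6.2, define a TEAE as an event with onset, or an increase in severity or seriousness of an event with pre-dose onset, from first exposure to concizumab until the last visit.

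In section 12.3, keep the single follow-up record, but for AEs with pre-dose onset require the date of the first increase in severity or seriousness on or after the first dose. Without that date the analysis cannot place the worsening relative to dosing, or assign it to the 24-week or 76-week time frame. The audit trail in section 13.1 dates the data entry and not the clinical change.

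Opening a new AE for the worsening would also work under the existing definition, but it leaves two records for one clinical event unless closure of the first is specified. The single-record form counts each event once.

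The cost is one sentence in each section, one extra date field for a few AEs, and possibly a slightly higher TEAE count. No assessment or visit is added.
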